## **8.4 Placebo**

The following IV placebos will be supplied by the Sponsor and utilized to maintain the blind. Further details are found in the Study Pharmacy Manual.

Drug Product	Route	Dosage Form/Strength
Moxifloxacin placebo	IV	0.9% NaCl for Injection (Given as alternating doses with IV moxifloxacin)
Linezolid matching placebo	IV	0.9% NaCl for Injection

The following oral placebo tablets/capsules will be supplied by the Sponsor: lefamulin placebo tablet, moxifloxacin placebo capsule, linezolid placebo capsule.

Further details may be found in the Study Pharmacy Manual.

## **8.5 Packaging and Labeling**

Study drugs will be packaged and labeled in accordance with the applicable regulatory authority requirements.

## **8.6 Storage of Study Drugs**

Access to all study drugs must be restricted to designated study personnel throughout the study.

Lefamulin concentrate vials and citrate buffered saline bags for dilution of lefamulin concentrate prior to administration will be provided in kits which will be stored between

+2°C and +8°C in a temperature monitored refrigerator. Intravenous bags containing moxifloxacin and linezolid must be stored at controlled room temperature (15 to 25°C).

Saline placebo must be stored at controlled room temperature (15 to 25°C).

Oral study medication will be supplied in blister packs. Four different blister packs will be provided:

- Lefamulin tablets and moxifloxacin placebo capsules
- Over-encapsulated moxifloxacin tablets and lefamulin placebo tablets
- Over-encapsulated linezolid tablets
- Linezolid placebo capsules

All blister packs containing oral study drug must be stored at controlled room temperature (15 to 25°C).

## 8.7 Product Accountability

The Investigator is responsible for study medication accountability, reconciliation, and record maintenance. In accordance with all applicable regulatory requirements, the Investigator or designated study site personnel must maintain study drug accountability records throughout the course of the study. This person(s) will document the amount of study drug received from the supplier, the amounts dispensed to subjects as well as lot numbers and expiration / retest date of study medications.

At the conclusion of the study, any unused study drug will be returned to either a Sponsor-designated recipient or destroyed at the site after discussion with the Sponsor. If no supplies remain, this will be recorded in the drug accountability section of the final monitoring report.

All unused study drug provided by the Sponsor will be retained for purposes of drug accountability. In addition, empty and partially used vials of lefamulin will be retained by the pharmacy for the purposes of drug accountability.

An unblinded member of the Sponsor's clinical operations staff (or designee) will check the supplies storage, dispensing procedures and records at regular intervals throughout the study.

## 9 STATISTICAL ANALYSIS

Inferential statistical analyses of the primary and secondary outcomes will be conducted as outlined below. Descriptive statistics, including the numbers and percentages for categorical variables, and the numbers, means, standard deviations, medians, minimums, and maximums for continuous variables will be provided. Additional statistical analyses, other than those described in this section, may be performed if deemed appropriate. A description of the statistical analysis performed on the study data will be outlined in the SAP.

As a consequence of differing regulatory requirements for the choice of primary efficacy analysis variable and statistical analyses of this study, 2 separate regional comprehensive SAPs will be prepared (FDA and EMA) and finalized before database lock and analysis of the data.

Exploratory evaluation of a variety of health utilization variables (e.g., length of hospital stay, duration of antibiotic therapy, discharge status, discharge destination) as well as a PRO instrument (SF-12) will be performed. Details for this exploratory analysis will be presented in a separate SAP and results will be presented in a stand-alone clinical study report.

## 9.1 Treatment Comparison of Interest

All comparisons will be for lefamulin versus comparator therapy (moxifloxacin ± linezolid).

## 9.2 Sample Size Determination

A total of 550 subjects will be randomized in this study (275 subjects in each treatment group). However, if based upon regulatory requirements additional subjects exposed to lefamulin are needed, up to 626 subjects may be enrolled. The total number of subjects included in this study is sufficient to achieve the primary and secondary study objectives based on statistical considerations.

Retrospective analyses of clinical study data for patients with CABP of varying severity indicate the point estimates for an ECR responder at Days 3-5 range from 72%-81% (FDA, 2011). Thus, it is reasonable to assume that in a prospective study of subjects with CABP, the proportion of subjects who are responders for ECR at  $96 \pm 24$  hours post first dose of study drug will be approximately 79%.

The primary efficacy analysis variables used for NI analyses for the Marketing Authorization Application (MAA) to the EMA will be the proportion of subjects with an IACR of Success at TOC in the mITT and CE-TOC Analysis Sets. In recent clinical studies, IACR success rates at the TOC Visit in the CE Analysis Set ranged from 77%-87% depending on the antibiotics under study and the severity of the CABP. The IACR success rate for subjects receiving moxifloxacin is 86% as reported in the prescribing information (AVELOX® [moxifloxacin] PI, 2013). Based on these data, an 85% IACR success rate in the CE-TOC Analysis Set was chosen for determination of the sample size. The success rate is expected to be about 5% lower in the mITT Analysis set. It is expected that <1% of subjects will be excluded from the mITT Analysis Set and thus, the sample size determination assumes the same number of subjects in the ITT and mITT Analysis Sets.

Utilizing an anticipated ECR responder rate of 79% in the ITT Analysis Set, and a one-sided alpha of 0.025, a sample size of 550 subjects (275 in each treatment group) provides >90% power to establish the NI of lefamulin to moxifloxacin for ECR using a NI margin of 12.5% at the ECA. Assuming an IACR success of 80% and 85% in the mITT and CE-TOC Analysis Sets, respectively, and a clinical evaluability rate of 80%, there is 80% power for demonstration of NI for IACR at the TOC Visit using a 10% NI margin. If the sample size is

increased to 626 subjects, it will provide >95% power for demonstration of NI for ECR and 85% power for demonstration of NI for IACR at the TOC Visit.

The calculated power in each analysis set for the primary and secondary outcomes is provided in Table 11 below.

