### **Statistical Methods:**

[figure not shown]
A 2-sided unstratified 95% confidence interval (CI) for the observed difference between treatment groups (lefamulin minus moxifloxacin) in ECR responder rates at  $96 \pm 24$  hours post first dose will be calculated using a continuity corrected Z-statistic. Non-inferiority for the primary efficacy analysis variable (FDA) will be concluded if the lower limit of the 2-sided 95% CI is greater than  $-12.5\%$  in the ITT Analysis Set.

For the efficacy outcome measure of IACR of Success at TOC in the mITT and CE-TOC Analysis sets, unstratified 95% CI will be calculated using a continuity corrected Z-statistic (FDA secondary efficacy outcome). For the primary analysis for the EMA, a stratified 2-sided 95% CI will be calculated using the method of Miettinen and Nurminen. Non-inferiority for the primary efficacy analysis variable (EMA) will be concluded if the lower limit of the 2-sided stratified 95 % CI is greater than  $-10\%$  for both the mITT and CE-TOC Analysis Sets.

The number and percentage of subjects with an ECR of Responder at  $96 \pm 24$  hours will also be presented for the microITT Analysis Set, and a 2-sided unstratified 95% CI for the difference in responder rate will be calculated using a continuity-corrected Z-statistic. However, the formal test of NI will be conducted in the weighted (based on the inverse variance of each effect size) pooled population from this study and a second study in CABP.

[figure not shown]
The incidence of treatment-emergent AEs (TEAEs), serious AEs (SAEs), deaths, and discontinuations of study drug due to an AE or SAE will be summarized by System Organ Class (SOC) and Preferred Term according to the Medical Dictionary for Regulatory Activities (MedDRA), by relationship to study drug, and by severity. The incidence of potentially clinically significant laboratory results, vital signs, and ECGs will be summarized.

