**Table 11. Power Calculations for the Primary and Secondary Efficacy Outcomes**

Analysis Set	Primary Outcome (FDA) (ECR 96 ± 24 h After the First Infusion of Study Drug)	Secondary Outcome (Investigator's Assessment of Clinical Response at TOC- Primary for EMA)	
	ITT	mITT	CE-TOC
N	550	550	440
Outcome Rate	79%	80%	85%
Evaluability Rate	NA	NA	80%
Power	93.8%	80.6%	80%

CE=clinically evaluable; ITT=intent to treat; mITT=modified ITT; TOC=test of cure

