Additional analyses of the primary efficacy analysis will be conducted. ECR will be assessed separately across the geographic regions, prior antibiotic use, and PORT risk class strata. For each geographic region, prior antibiotic use, and PORT risk class stratum, a 2-sided 95% CI for the observed difference in ECR responder rates will be calculated for the ITT Analysis Set. Sensitivity analyses of ECR include determination of an adjusted 95% CI (adjusted for the randomization stratification factors) and considering all subjects with missing data (i.e., Indeterminates) at  $96 \pm 24$  hours after the first dose of study drug as responders for ECR (these subjects are considered non-responders in the primary analysis). For the second sensitivity analysis, an unstratified 95% CI will be computed for the difference in the responder rates between lefamulin and moxifloxacin. Subgroup analyses of the primary efficacy outcome will also be conducted for descriptive purposes and will be detailed in the SAP.

For the EMA primary analysis (secondary analysis for the FDA), the number and percentage of subjects in each treatment group with an IACR of Success, Failure and Indeterminate (by definition Indeterminates are not included in the CE-TOC Analysis Set) at TOC will be reported in the mITT and CE-TOC Analysis Sets. Subjects who have an IACR of Failure at EOT will be considered to have an IACR of Failure at TOC. The primary analysis for the EMA will utilize 2-sided adjusted (for the randomization stratification factors) 95% CIs calculated using the method of Miettinen-Nurminen. If the lower limit of the 95% CI for the difference in success rates in both the mITT and CE-TOC Analysis Sets is greater than -10%, the NI of lefamulin to moxifloxacin will be concluded. Two-sided unstratified 95% CIs will be calculated for the difference in success rates at TOC in the mITT and CE-TOC Analysis Sets (FDA secondary outcome).

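### Section 9.2 and the synopsis give single-set IACR power (80% at 550, 85% at 626) as the power to show non-inferiority, but the EMA rule needs both sets and its power is 5 to 7 points lower on the same test

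*Protocol*

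**What the plan says.** Section 9.2 assumes IACR success of 80% in the mITT set and 85% in the CE-TOC set, with 80% of subjects clinically evaluable. On that basis it states that "there is 80% power for demonstration of NI for IACR at the TOC Visit using a 10% NI margin" at 550 subjects, and "85% power for demonstration of NI for IACR at the TOC Visit" at 626. The Statistical Considerations part of the synopsis gives the same two figures.

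Table 11 is introduced as showing "The calculated power in each analysis set for the primary and secondary outcomes". For 550 subjects it lists 80.6% for mITT (N = 550) and 80% for CE-TOC (N = 440). It has no entry for 626.

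Section 9.6.1 sets the EMA decision rule. Non-inferiority is concluded if the lower limit for the difference in "success rates in both the mITT and CE-TOC Analysis Sets is greater than -10" percent. The analysis uses "2-sided adjusted (for the randomization stratification factors) 95% CIs calculated using the method of Miettinen-Nurminen". The Statistical Methods part of the synopsis likewise requires the limit to clear -10% "for both the mITT and CE-TOC Analysis Sets".

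**The concern.** Under the protocol's own rule, showing non-inferiority on IACR for the EMA means passing two tests on overlapping sets. The probability of passing both is lower than the probability of passing either, unless the two tests always agree. The text nevertheless gives one figure per sample size and describes it as the power to show non-inferiority on IACR, although each figure is a one-set power.

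A reader of the synopsis, or of the 626 sentence in Section 9.2, will therefore take a per-set figure as the power for an EMA primary objective. Section 9.2 also says that the sample size is sufficient for the primary objectives, and this figure is part of the support for that statement.

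**Working it through.** **Inputs (Section 9.2 and Table 11).** One-sided alpha 0.025; margin 10%; success 80% in mITT and 85% in CE-TOC; 80% evaluable; 275 or 313 per arm in mITT, hence 220 or 250.4 in CE-TOC. Taken as assumptions: no true difference, and evaluability independent of arm.

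**Step 1: reproduce the printed figures.** Section 9.2 does not name the test. A Z-test with unpooled variance and continuity correction gives

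power = Φ[(0.10 − 1/n) / √(2p(1−p)/n) − 1.96].

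- mITT, n = 275: (0.10 − 0.00364)/0.03411 − 1.96 = 0.865, power 80.65% (Table 11: 80.6%).
- CE-TOC, n = 220: (0.10 − 0.00455)/0.03405 − 1.96 = 0.844, power 80.06% (Table 11: 80%).
- At 626: mITT 85.7%, CE-TOC 85.3% (stated 85%).
- ECR with rate 79% and margin 12.5%: 93.75% at 550 (stated 93.8%) and 96.3% at 626 (stated above 95%).

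Without the correction, IACR at 550 would be 83.4% and 83.6%, which does not match. One formula explains all the stated figures, and each IACR figure is a single-set power.

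**Step 2: correlation between the two tests.** CE-TOC is nested in the full set. The assumed rates imply success of (0.80 − 0.80 × 0.85)/0.20 = 60% among non-evaluable subjects. The correlation between the two estimated differences is 0.80 × SE(CE-TOC)/SE(mITT) = 0.80 × 0.03405/0.03411 ≈ 0.80.

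**Step 3: power to pass both sets.** The continuity-corrected rows use a bivariate normal calculation. The Miettinen-Nurminen rows come from simulation of 1,000,000 trials per size, unstratified, with random evaluability.

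| Test | Total N | mITT | CE-TOC | Both sets |
|---|---|---|---|---|
| Continuity-corrected Z | 550 | 80.6% | 80.1% | 73.3% |
| Continuity-corrected Z | 626 | 85.7% | 85.3% | 79.7% |
| Miettinen-Nurminen | 550 | 83.2% | 82.8% | 76.6% |
| Miettinen-Nurminen | 626 | 87.7% | 87.3% | 82.4% |

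Measured from the lower single-set power, the loss is 6.8 and 5.5 points on the first test, and 6.2 and 5.0 points on the second. If exactly 80% of each arm is evaluable rather than 80% on average, the Miettinen-Nurminen both-sets values are 77.6% and 83.0%.

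**Step 4: sensitivity.**

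- *Correlation 0.7 to 0.9.* With the correction, both-sets power is 71.7-75.4% at 550 and 78.5-81.4% at 626. Without it, by normal approximation, it is 75.8-79.1% and 81.8-84.3%. All values are below the printed 80% and 85%.
- *Success rate.* Section 9.2 reports that "IACR success rates at the TOC Visit in the CE Analysis Set ranged from 77%-87" percent. With mITT 5 points lower than CE-TOC, the Miettinen-Nurminen both-sets power at 550 and 626 is 64.5% and 70.8% for a CE rate of 77%, 71.4% and 77.5% for 82%, and 80.7% and 86.0% for 87%. At CE rates of 82-87%, both-sets power stays about 4-8 points below per-set power.
- *Stratification.* The planned interval is adjusted, but no gain in precision is stated. By normal approximation without the correction, both-sets power is 77.2% at 550 and 82.9% at 626 with no gain. Reaching 80% and 85% needs variance reductions of about 6.0% and 5.2%.
- *Total size for 80% both-sets power.* About 630 on the continuity-corrected test, and about 592 with Miettinen-Nurminen.

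**The case against.** The strongest reply is that no printed number is miscalculated and that, for 550, Section 9.2 shows its basis. The sentence names the two sets, and Table 11 gives a separate power for each. That stands for the table, so a careful reader of Section 9.2 can see that the 550 figure is per set. It does not cover the synopsis or the 626 sentence, which carry no such label, and no passage gives the power of the rule that decides the EMA claim.

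A second reply is that the loss of 5 to 7 points pairs the EMA rule with a test that the EMA analysis does not use. This is fair. Against the printed figures, the shortfall under the planned interval is only about 3 points, because two changes work in opposite directions. Dropping the continuity correction adds about 3 points at 550 and 2 at 626; requiring both sets takes away about 6 and 5. Stratification could recover the rest, but the protocol states no gain.

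A third reply is that the interim re-estimation protects power. Section 9.9 aims at adequate power for both the FDA and EMA outcomes, and could lead to an increase separate from the 626 allowed for exposure reasons. The basis it states for the calculation, however, is the blinded ECR rate. It gives no two-set IACR power, and the committee charter is not shown.

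**Conclusion.** The concern holds and should be fixed. The per-set arithmetic is right, but 80% and 85% are presented as the power of a conclusion that they do not measure. Both-sets power is about 73% and 80% on the test that reproduces Table 11, and about 77% and 82-83% under the planned interval without any stratification gain. At 550, the chance of missing the EMA objective when the two treatments are equally effective is thus about 23-27%, not 20%.

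These values rest on the protocol's rates and evaluability, no true difference, evaluability independent of arm, and the implied correlation of 0.80. The level moves with the assumed success rate. The decision rule, the type I error and the FDA endpoint are untouched.

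**What to change.** In Section 9.2 and the synopsis, label 80% (550) and 85% (626) as the power in each analysis set, and name the test behind them. They reproduce with a continuity-corrected Z-test, which the sponsor should confirm.

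In Section 9.2, the synopsis and Table 11, give per-set and both-sets IACR power at 550 and 626 on one named test, preferably the planned Miettinen-Nurminen interval. Unstratified, that is about 83% per set and 77% for both sets at 550, and about 87-88% and 82-83% at 626. State the assumptions, including the correlation of about 0.80 and any stratification gain. Do not set a both-sets figure from one test beside per-set figures from another.

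The cost is two relabelled sentences and recalculated IACR columns in Table 11, with a both-sets entry and the 626 case added. The stated EMA power becomes about 3 points less favourable under the planned test. No change of enrolment is proposed.

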**Table 11. Power Calculations for the Primary and Secondary Efficacy Outcomes**

Analysis Set	Primary Outcome (FDA) (ECR 96 ± 24 h After the First Infusion of Study Drug)	Secondary Outcome (Investigator's Assessment of Clinical Response at TOC- Primary for EMA)	
	ITT	mITT	CE-TOC
N	550	550	440
Outcome Rate	79%	80%	85%
Evaluability Rate	NA	NA	80%
Power	93.8%	80.6%	80%

CE=clinically evaluable; ITT=intent to treat; mITT=modified ITT; TOC=test of cure

## 9.3 Analysis Populations

### 9.3.1 Intent-to-Treat Analysis Set (ITT)

The ITT Analysis Set will consist of all randomized subjects regardless of whether or not the subject received study drug. A subject is considered randomized when an IRT-generated randomization number has been assigned.

### 9.3.2 Modified Intent-to-Treat Analysis Set (mITT)

The mITT Analysis Set will consist of all randomized subjects who receive any amount of study drug. Subjects are analyzed based on the randomized (i.e., assigned) treatment group.

### 9.3.3 Safety Analysis Set

The Safety Analysis Set will consist of all randomized subjects who receive any amount of study drug. Subjects are analyzed based on the study drug actually received. All safety analyses will be conducted in this population.

### 9.3.4 Microbiological Intent-to-Treat Analysis Set (microITT)

The microITT Analysis Set will consist of all subjects in the ITT Analysis Set who have at least one baseline “typical” bacterial pathogen known to cause CABP, *Legionella pneumophila* from an appropriate microbiological specimen, or who have CABP caused by *Mycoplasma pneumoniae* or *Chlamydophila pneumoniae*.

### 9.3.5 Clinically Evaluable Analysis Set

The CE Analysis Sets (CE-EOT, CE-TOC, and CE-LFU Analysis Sets) will be a subset of the ITT Analysis Set that will include subjects who meet the criteria for CABP described in Inclusion Criteria Nos. 3 - 7, and who received at least the pre-specified minimal amount of the intended dose of study drug and duration of treatment, do not have an indeterminate response based on the IACR (at EOT for the CE-EOT Analysis Set, at TOC for the CE-TOC Analysis Set, and at LFU for the CE-LFU Analysis Set), did not receive concomitant antibacterial therapy (other than adjunctive linezolid) that is potentially effective against CABP pathogens (except in the case of clinical failure) from the first dose of study drug through the EOT Visit (CE-EOT Analysis Set), through the TOC Visit (CE-TOC Analysis Set), and through the LFU Visit (CE-LFU Analysis Set), and for whom there are no other confounding factors that interfere with the assessment of the outcome.

### 9.3.6 Microbiologically Evaluable Analysis Set

The ME Analysis Set (ME-EOT, ME-TOC, and ME-LFU) will include all subjects who meet the criteria for inclusion both the microITT and CE-EOT (ME-EOT) Analysis Set, the CE-TOC (ME-TOC) Analysis Set, or the CE-LFU (ME-LFU) Analysis Set.

### 9.3.7 Pharmacokinetic Analysis Set

All subjects who receive any amount of study drug will be included in the formal analysis of PK parameters providing they have at least 1 evaluable PK sample.

## 9.4 Criteria for Evaluation

### 9.4.1 Primary Efficacy Analysis Variable

The primary efficacy variable (FDA) is the proportion of subjects in the ITT Analysis Set with an ECR of Responder at  $96 \pm 24$  hours post first dose.

Subjects will be defined as an ECR of Responder if the following 4 criteria are met:

- Alive
- Improvement in at least 2 of the 4 cardinal symptoms of CABP (Section 6.10), the subject presented with at Baseline. Improvement is defined as a decrease by at least 1 level of severity.
- No worsening of any of the 4 cardinal symptoms of CABP. Worsening is defined as an increase by at least 1 level of severity of any symptom.
- Did not receive a concomitant antibiotic (other than adjunctive linezolid) for the treatment of CABP.

The primary efficacy variable for the EMA and secondary efficacy variable for the FDA is the proportion of subjects with an IACR of Success at TOC in the mITT and CE-TOC Analysis Sets (see Section 6.11). An IACR of Success is defined as a subject whose clinical

signs and symptoms have resolved or improved such that no additional antibacterial therapy is administered for the treatment of the current episode of CABP. Subjects who have an IACR of Failure at EOT will not have an IACR assessed at TOC and will be considered to have an IACR of Failure at TOC.

## 9.4.2 Secondary Efficacy Analysis Variables

### 9.4.2.1 Clinical Outcome

The Investigator's Assessment of Clinical Response will be evaluated in the microITT and ME-TOC Analysis Sets at TOC as described in Section 6.11. ECR will be evaluated in the microITT Analysis Set. All-cause mortality will be evaluated in the ITT Analysis Set.

ECR plus improvement in vital signs (i.e., body temperature, blood pressure, heart rate, respiratory rate), if abnormal at baseline will be evaluated in the ITT Analysis set. If vital signs are normal at baseline (i.e., not abnormal as per the definitions below), none can have worsened.

Abnormal vital signs are defined as:

- Fever: [defined as body temperature >38.0 degrees Celsius (100.4 degrees Fahrenheit) measured orally, >38.5 degrees Celsius (101.3 degrees Fahrenheit) measured tympanically, or >39.0 degrees Celsius (102.2 degrees Fahrenheit) measured rectally]
- Hypothermia: [defined as body temperature <35.0 degrees Celsius (95.0 degrees Fahrenheit) measured orally, <35.5 degrees Celsius (95.9 degrees Fahrenheit) measured tympanically, or <36.0 degrees Celsius (96.8 degrees Fahrenheit) measured rectally]
- Hypotension: defined as systolic blood pressure <90 mmHg
- Tachycardia: defined as heart rate >100 bpm
- Tachypnea: defined as respiratory rate > 20 breaths/min

